6.4. Assessment of Safety

6.4.1. Safety parameters

(Serious) Adverse Events (see section 9)

- Vital signs: pulse, blood pressure, temperature, and weight
- Physical examination including inspection of the vaccination site
- Clinical laboratory evaluations:
 - Hematology: white blood cell (WBC), hemoglobin (Hb), platelet count, absolute neutrophil count (ANC), absolute lymphocyte count (ALC)
 - Chemistry: AP, total bilirubin, AST/ SGOT, ALT/ SGPT, LDH, and uric acid, CRP, sodium, potassium, calcium, blood urea nitrogen, creatinine, glucose, C-reactive protein
- Concomitant medications
- (S)AEs by NCI CTCAE Version 5.0 and as in appendix 14.5

6.4.2. Methods and Timing for Assessing, Recording, and Analysing Safety Parameters

Serial measurements of safety will be performed at screening and at scheduled intervals throughout the duration of the study as outlined in table 1. All scheduled visits have a \pm 1 day window unless otherwise stated. Abnormalities will be captured as protocol deviations. Lab abnormalities grade 1-2 are only considered AE if they fulfill one of the following criteria:

- Accompanied by clinical symptoms.
- Requiring a change in concomitant therapy (e.g. addition or change in a concomitant medication, therapy or treatment).

All Grade 3-4 laboratory abnormalities fulfilling the criteria for an SAE will be reported as SAEs and will be recorded on the AE pages of the CRF; however, those that are not deemed by the investigator to be part of a diagnosis or syndrome will not be reported to the Health Authorities in an expedited manner. Cause of death is to be recorded in the CRF and the subject's medical record.

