9.1.5. Serious Adverse Event and Serious Adverse Reaction

AEs are classified as "non-serious" or "serious".

A serious adverse event (SAE) is one that at any dose:

- Results in death.
- Is life-threatening (the term life-threatening refers to an event in which the subject was at risk of death at the time of event and not to an event which hypothetically might have caused death if it was more severe).
- Requires subject hospitalization or prolongation of existing hospitalization.
- Results in persistent or significant disability/ incapacity.
- Causes a congenital anomaly / birth defect.
- Is medically significant (e.g. suspected transmission of an infectious agent via medicinal product). Moreover, there are other situations - such as

Protocol		
Protocol code and Short Title:	P-pVAC-SARS-CoV-2	Date/Version:08.03.2021/V1.4

important medical events that may not be immediately life threatening or result in death or hospitalization, but may jeopardize the patient or may require intervention to prevent one of the other outcomes listed above. Important medical event [ICH E2A; EMA/155528/2018]: Examples of such events are intensive treatment in an emergency room or at home for allergic bronchospasm; blood dyscrasias or convulsions that do not result in hospitalisation; development of drug dependency or drug abuse (Important medical event terms list (MedDRA \geq version 23.0).

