Unknown	The outcome is unknown or implausible and the information cannot be supplemented or verified.

9.3.3. *Action taken*

No action will be taken with regards to the IMP as the vaccine is applied only once.

9.3.4. *Sponsors Assessment of the SAEs*

All SAE will be subject to a second assessment by the trial Sponsor or authorized second assessors, e.g. CI.

The second assessor will fill out a 'Second Assessment Form' for each SAE containing.

- Event serious yes/no
- Relationship between SAE and IMP/study procedure
- Expectedness of SAE according to the reference document: IB CoVac-1 peptide vaccine V1.0 dated 22.5.2020.
- Benefit / risk assessment for the trial regarding change as a result of SAE.

9.3.5. *Follow-up of Initial Report*

Information not available at the time of the initial report (e.g. end date for the AE or laboratory values received after the report) must be documented on a "Serious Adverse Event" form with the box "Follow-up" checked under "Report type".

All volunteers who have AEs, whether considered associated with the use of the investigational products or not, must be monitored to determine the outcome as far as possible. The clinical course of the AE will be followed up according to accepted standards of medical practice even after the end of the period of observation, until a satisfactory explanation is found or the investigator considers it medically justifiable to terminate follow-up. Should the AE result in death, a full pathologist's report should be supplied, if possible.

The sponsor will identify missing information for each SAE report and will require follow up information in regular intervals from the investigators until all queries are resolved or no further information can be reasonably expected. All responses to queries and supply of additional

information by the investigator should follow the same reporting route and timelines as the initial report.

9.3.6. *Exception of reporting*

As this is a prophylactic vaccination trial with application of CoVac-1 in healthy adults, no exception of reporting for AEs are made.

9.3.7. *Suspected Unexpected Serious Adverse Reaction (SUSAR)*

SAEs that are both suspected, i.e. possibly related to IMP, and ‘unexpected’, i.e. the nature and/ or severity of which is not consistent with the applicable product information are to be classified as Suspected Unexpected Serious Adverse Reactions (SUSARs).

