In case that either the investigator who primarily reported the SAE, or the second assessor classify the SAE as ‘suspected’ (i.e. *not as "definitely not related to IMP"*) and the SAE is also unexpected, it will be categorized as a SUSAR.

All SUSARs are subject to an expedited reporting to the responsible ethics committee(s), the competent higher federal authority (PEI) and to all participating investigators.

9.3.8. *Expedited Reporting to the Regulatory Authorities*

Fatal and life-threatening SUSARs

The competent authority (PEI) and the EC responsible must be informed by the Sponsor of all fatal or life-threatening SUSARs. This must be done immediately, at the latest seven calendar days after becoming aware of the minimum criteria for reporting. In all cases, attempts must be made to obtain further relevant information, which must be supplied to the competent authority and the EC in overall charge within a further eight days. Furthermore, if a trial subject dies, this information must be additionally passed on to the EC responsible for the region in which the death occurred.

SUSARs that are not fatal or life-threatening

The authority (PEI) and the EC responsible will be informed without delay by the sponsor or CI of all SUSARs, at the latest within 15 calendar days of becoming aware of the minimum criteria for reporting. Further relevant details will be passed on as soon as possible.

If the information at the time of reporting is incomplete, further information to enable adequate assessment of the case will be requested from the reporter or other available sources.

Protocol		
Protocol code and Short Title:	P-pVAC-SARS-CoV-2	Date/Version:08.03.2021/V1.4

9.4. *Examination and Report of Changes in the Risk to Benefit Ratio*

Without delay, and at the latest within 15 days of the decision for the need to do so, the Sponsor / CI will inform the competent authority (PEI), the EC responsible of any events or factors that could result in a review of the risk-benefit ratio of the IMP. These consist especially of:

- Individual reports of expected serious ADRs with an unexpected outcome.
- A clinically relevant increase in the rate of occurrence of expected ADRs.
- SUSARs in trial subjects who have already completed the follow-up period of the clinical trial ("end-of-trial visit").
- Factors emerging in connection with trial conduct or the development of the IMP that may affect the safety of persons concerned.

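### Section 6.4.2 bars expedited reporting of isolated Grade 3-4 laboratory SAEs without sparing those that are SUSARs, which sections 9.3.7, 9.3.8 and 10.7 require to be reported

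*Supplement*

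**What the plan says.** All references are to the latest protocol, V1.4 of 08.03.2021.

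Section 6.4.2 contains two linked rules. The first is inclusive: "All Grade 3-4 laboratory abnormalities fulfilling the criteria for an SAE will be reported as SAEs", and they are entered on the AE pages of the CRF. The second takes some of them out of fast reporting: those "not deemed by the investigator to be part of a diagnosis or syndrome will not be reported to the Health Authorities" on an expedited basis. Nothing in the sentence reserves events that are related or unexpected, and it does not refer to section 9.3.

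Section 9.3.7 defines a SUSAR by two properties only, opening with "SAEs that are both suspected, i.e. possibly related to IMP, and" and then adding that the nature or severity does not fit the product information. It excludes no type of event. It lets one of two people trigger the classification: "In case that either the investigator who primarily reported the SAE, or the second assessor classify the SAE as" suspected, meaning anything short of definitely unrelated, and the event is also unexpected, it is a SUSAR. On the consequence it says "All SUSARs are subject to an expedited reporting to the responsible ethics committee(s"), to PEI and to all participating investigators.

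Section 9.3.8 sets the deadlines: 7 calendar days for fatal or life-threatening SUSARs and 15 calendar days for the others. Section 10.7 states again that the ethics committee and PEI are informed of all SUSARs.

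**The concern.** The exemption in 6.4.2 turns on whether a laboratory value belongs to a diagnosis or syndrome. The duty in 9.3.7-9.3.8 turns on suspicion of a causal link and on expectedness. These are different questions, so one event can satisfy both. When it does, 6.4.2 tells the reader not to expedite and 9.3.7-9.3.8 tell the reader to do so within 7 or 15 days.

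What is at stake is timely notice to the authority of a possible signal. Section 5.7.2.2 says that XS15 had never been used in a clinical trial before. An abnormal value without a diagnosis is one form in which an unforeseen effect can first appear. An SAE associated with CoVac-1 is also the critical event on which the stopping rule in section 8.6 depends. An event that matters this much to the trial should not fall under two opposite reporting instructions.

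**Working it through.** No arithmetic underlies either rule, so the check is a comparison of the texts.

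**Step 1: where the rules overlap.** Take Grade 3-4 laboratory abnormalities that meet the SAE criteria and classify each by three yes/no properties: isolated (not attached by the investigator to a diagnosis or syndrome), suspected, unexpected. That gives 2 × 2 × 2 = 8 kinds of event.

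| Isolated | Suspected and unexpected | 6.4.2 | 9.3.7-9.3.8 | Result |
|---|---|---|---|---|
| No | No (3 kinds) | No bar | No SUSAR report due | Agree |
| No | Yes (1 kind) | No bar | Report in 7 or 15 days | Agree |
| Yes | No (3 kinds) | Not expedited | No SUSAR report due | Agree |
| Yes | Yes (1 kind) | Not expedited | Report in 7 or 15 days | **Conflict** |

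The rules conflict for 1 of the 8 kinds. This is a count of logical cases and says nothing about frequency.

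**Step 2: whether that cell can be occupied.**
- Suspicion has a low threshold in 9.3.7: anything not definitely unrelated to the vaccine.
- On expectedness, the solicited reactions in section 9.1.2 are local reactions and systemic symptoms, with no laboratory finding. The Part I results in section 5.7.2.1 name none either. The reference document for expectedness in section 9.3.4 is the Investigator's Brochure, which is not shown. On the protocol's own lists, a related serious laboratory event would be unexpected; the brochure could change that.
- Table 1 schedules hematology and blood chemistry at every visit from V1 to V5, so isolated findings can come to light.

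The cell is therefore reachable. The documents give no rate from which to say how often.

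**Step 3: who decides.** Under 6.4.2 the investigator's judgement alone takes the event out of expedited reporting. Under 9.3.7 the second assessor alone can classify it as suspected. Suppose the investigator regards a value as isolated and the second assessor regards the event as suspected and unexpected. Section 6.4.2 then says not to expedite and 9.3.7 says to expedite, and the protocol does not say which prevails.

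**Step 4: whether another passage reconciles them.** Section 6.4.1 refers (S)AEs to section 9 in general. Neither 6.4.2 nor 9.3.7, 9.3.8 or 10.7 mentions the other rule or sets an order of precedence.

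**The case against.** The strongest reply is that section 9 is the dedicated reporting chapter and its SUSAR rules would govern in practice. Every SAE goes to the sponsor's representative within 24 hours (9.3.1). Each then receives a second assessment of relatedness, expectedness and benefit-risk (9.3.4), and the diagnosis-or-syndrome test plays no part in that assessment. The DSMB is told as soon as a vaccine-related SAE occurs (9.4.1), and the statistical center checks for critical events daily (8.2). Section 9.4 requires notice to PEI and the ethics committee within 15 days of the decision that an event could lead to a risk-benefit review. A fatal or life-threatening SUSAR during the period covered by the holding rules also leads to notice to both bodies (6.5).

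Most of this stands, and it limits the consequence. It does not remove the conflict, because no passage gives section 9 precedence over the explicit instruction in 6.4.2.

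A reader might also infer more than the texts support:
- **That every isolated serious laboratory event is affected.** For those that are unrelated or expected, 9.3.8 requires no expedited SUSAR report, so the rules agree.
- **That section 9.3.6 is itself contradicted.** Its statement that "no exception of reporting for AEs are made" concerns AE reporting in general. Section 6.4.2 still has these events reported as SAEs.
- **That section 9.1.5 supplies a clear example.** It lists "blood dyscrasias or convulsions that do not result in hospitalisation" as important medical events, but a blood dyscrasia may itself count as a diagnosis and so fall outside the exemption.
- **That the authority would first learn of the event from the annual safety report.** That is a worst case, requiring 6.4.2 to prevail over 9.3.7, 9.3.8 and 10.7 and section 9.4 not to be triggered.
- **That one such event ends the trial.** A related event reaches the formal stopping rule (8.2, 8.6), but section 6.8 says only that termination must be considered.

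**Conclusion.** The concern holds for a defined subset: Grade 3-4 laboratory SAEs that the investigator regards as isolated and that are also suspected and unexpected. For these, 6.4.2 forbids what 9.3.7-9.3.8 require within 7 or 15 calendar days and what 10.7 repeats as a duty to inform. The sections also differ on whose judgement counts. The subset may be small; its size cannot be derived from the documents and depends partly on the brochure.

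The effect is limited to expedited notice to the authority. Recording of the event as an SAE, notice to the sponsor and the DSMB, the primary endpoint and the stopping rule do not depend on the clause. The conclusion assumes that 6.4.2 is applied as written and that no document outside those shown sets an order of precedence. Within those limits the text is wrong as it stands and should be corrected, because a reader who follows 6.4.2 literally would withhold a report that section 9.3 requires.

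**What to change.** Reconcile section 6.4.2 with sections 9.3.7, 9.3.8 and 10.7. Either delete the clause on expedited reporting from 6.4.2, or limit it in words to laboratory SAEs that are not SUSARs. In both cases refer to 9.3.7-9.3.8 for classification and timing, so that either assessor's judgement counts here as it does there.

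The cost is one sentence and, at most, a few additional expedited reports. No endpoint, sample size, visit or analysis changes.

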6.5. Vaccination holding rules

Safety holding rules for each subject will apply throughout the study period until interim safety analysis (V4). Vaccination of further study subjects in the consecutive study phase will not occur until a safety review has been conducted by the DSMB and only by approval a holding rule can be resolved. If a holding rule is activated, the PI will inform the Sponsor within 48 hours. The Sponsor will inform the responsible authorities (PEI and EC).

If the DSMB permits the resumption of injections, a formal request with pertinent data must be submitted to ECs and PEI. The discontinuation of a holding rule should be communicated to all entities in the same manner and timeframe as described above.

The DSMB safety review will consider:

- The relationship of the AE or SAE to the vaccine or other possible causes of the event.
- If appropriate, additional screening or laboratory testing for other volunteers to identify those who may develop similar symptoms and alterations to the current informed consent form will be discussed.

All injected volunteers will be followed for safety until resolution or stabilization (if determined to be chronic sequelae) of their AE.

The holding rules are as follow:

Protocol		
Protocol code and Short Title:	P-pVAC-SARS-CoV-2	Date/Version:08.03.2021/V1.4

- **Solicited local ADRs:** If more than 30% of injections are followed by Grade ≥ 3 solicited swelling or pain or Grade 4 redness (first occurrence at any time after vaccination) and persisting at Grade 3 (swelling or pain)/4 (redness) for > 48 h to maximum 72 hours depending upon symptom severity and kinetics.
- **Solicited systemic AEs:** If more than 25% of injections are followed by Grade 3 solicited systemic AE beginning within 3 days after study injection (day of injection and 2 subsequent days) and persisting at Grade ≥ 3 for > 48 h to maximum 72 hours depending upon symptom severity and kinetics.
- **Unsolicited AEs:** If more than 25% of volunteers develop a Grade ≥ 3 unsolicited AE (including laboratory AE and physical observations) that is considered probably or definitely related to injection and persists at Grade 3 for > 48 to maximum 72 hours depending upon symptom severity and kinetics.
- A suspected unexpected serious adverse drug reaction (SUSAR) occurs that is life-threatening or results in death.

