1.1.3.2. Dose rationale for XS15

The molecular mode of action of both the Pam3Cys conjugates and XS15 is an activation of immune cells via the toll-like receptor TLR1/2. These immune cells are mainly found in the blood and lymphoid tissues. Desired as well as toxic effects are therefore to be expected above all and presumably exclusively due to the XS15-TLR1/2 interaction with these cells, in particular through an over activation of these cells, which could then lead to a so-called cytokine release syndrome. The dose of XS15 is based on an in vitro assay that investigated both potential toxicity as well as efficiency. In these assay 10 µg/ml XS15 was shown to be the most efficient dose for the stimulation of immune cells (for more details please refer to the IB of XS15). The following considerations regarding the concentration of XS15 after a subcutaneous administration are the basis of dose finding: When used with Montanide ISA 51

Protocol		
Protocol code and Short Title:	P-pVAC-SARS-CoV-2	Date/Version:08.03.2021/V1.4

VG in a total volume of 500 µl suspension, a granuloma forms rapidly at the injection site, which has a volume of estimated 2 ml. This granuloma further increases up to 8ml on day 17 after vaccination⁵⁸. Thus, the initial local concentration of XS15 is maximally 50 µg/ml which is reduced soon thereafter to 25 µg/ml (50µg in 2 ml) and soon thereafter is diluted even more, since the granuloma increases more, so that a concentration of 10 microgram/ml will soon be reached. Further dilution will follow with the granuloma increase to 6,25mg/ml (50 µg in 8ml). Based on this in vitro experiments and considerations the dose of 50 µg was selected for further in vitro and in vivo toxicity evaluation as well as for first in vivo vaccination experiments.

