In the toxicity study of mice, a dose of 50 µg XS15 in Montanide, applied locally s.c., did not reveal any toxicity beyond the long known and expected toxicity of Montanide alone. Therefore, this study proves that XS15 has no local and above all no systemic toxicity under this application method up to the above mentioned dose (for more details please refer to the IB of XS15). Furthermore, considering systemic toxicity of XS15 50µg after s.c. injection the following considerations were made: If this dose (in the absence of Montanide ISA 51 VG) is immediately distributed in the blood (6l), a maximum blood concentration of 0.008 µg/ml would be expected. At a concentration of 0.008 µg/ml no measurable reaction (stimulation of immune cells) is detected in the above described in vitro test.

When used with Montanide, the formation of a granuloma at the injection site, which has a depot effect for peptides, means that a gradual release of these peptides or XS15 into the blood can be expected. Therefore, the actual blood concentration of XS15 after administration of 50 µg in a Montanide/water emulsion is likely to be much lower than the maximum concentration of 0.008 µg/ml described above. Therefore, a systemic toxic effect of XS15 is not expected at a dose of 50 µg s.c. with or without Montanide.

1.1.3.3. *Dose rationale for Montanide ISA 51 VG*

Montanide™ ISA 51 VG has been used in about 300 clinical trials from phase I to phase III which represents more than 19 000 vaccines. In addition, Montanide™ ISA 51 VG has been approved in a commercial vaccine against non-small cell lung cancer (NSCLC).

Dosing of 0,25ml after 50/50 mixture with peptides is based on two published clinical studies evaluating influenza vaccines in more than 2500 donors showing high immunogenicity and a good safety profile^{87 88}. Detailed information on preclinical and clinical safety data for Montanide ISA 51 VG could be found in the respective IB as well as in the attached “Human application form for Montanide ISA 51 VG”.

Protocol		
Protocol code and Short Title:	P-pVAC-SARS-CoV-2	Date/Version:08.03.2021/V1.4

1.1.3.4. *Rationale for one dose schedule*

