2.1.1. Primary Endpoint

The nature, frequency, and severity of AEs and/or SAEs associated with administration of CoVac-1:

- Solicited: ADRs/AEs occurring from the time of each injection throughout 28 days following the procedure, facilitated by use of a volunteer diary
- Unsolicited: AEs from the time of injection throughout 56 days following injection
- SAEs from the time of injection until the final study visit for each subject
- Incidence of AESIs until the final study visit for each subject

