14.5. Intensity of solicited and unsolicited local and systemic adverse events

Local solicited AEs	CTCAE Term	Grade 0 Normal	Grade 1 Mild	Grade 2 Moderate	Grade 3 Severe	Grade 4 Potentially life-threatening
Erythema	Injection site reaction	< 25 mm	25-50mm Tenderness with or without associated symptoms (e.g., warmth, erythema, itching)	51-100mm Pain; lipodystrophy; edema; phlebitis	> 100mm Ulceration or necrosis; severe tissue damage; operative intervention indicated	Life-threatening consequences; urgent intervention indicated
Swelling		< 25 mm	25-50 mm and does not interfere with activity	> 50 mm or interferes with activity	Prevents daily activity	Necrosis
Pain	Injection site reaction	None	Tenderness with or without associated symptoms (e.g., warmth, erythema, itching) Does not interfere with activity	Pain; lipodystrophy; edema; phlebitis Interferes with activity	Ulceration or necrosis; severe tissue damage; operative intervention indicated Prevents daily activity	Life-threatening consequences; urgent intervention indicated Emergency room visit or hospitalization

Protocol

Protocol code and Short Title:

P-pVAC-SARS-CoV-2

Date/Version:08.03.2021/V1.4

Systemic solicited AEs	CTCAE Term	Grade 0	Grade 1	Grade 2	Grade 3	Grade 4
Fever		None	38.0° - 39.0°C	≥ 39.0° - 40.0°C	≥ 40.0°C for ≤ 24 hours	≥ 40.0°C for ≥ 24 hours
Chills		None	Mild sensation of cold; shivering; chattering of teeth	Moderate tremor of the entire body; narcotics indicated	Severe or prolonged, not responsive to narcotics	-
Myalgia (described to the subject as generalized muscle aches)		None	Mild pain	Moderate pain; limiting instrumental ADL	Severe pain; limiting self care ADL	-
Arthralgia (described to the subject as generalized joint aches)			Mild pain	Moderate pain; limiting instrumental ADL	Severe pain; limiting self care ADL	-
Fatigue			Fatigue relieved by rest	Fatigue not relieved by rest; limiting instrumental ADL	Fatigue not relieved by rest, limiting self care ADL	-
Headache		None	Mild pain	Moderate pain; limiting instrumental ADL	Severe pain; limiting self care ADL	-
Gastrointestinal symptoms (nausea, vomiting, abdominal pain, and/or diarrhea)	nausea	None	Loss of appetite without alteration in eating habits	Oral intake decreased without significant weight loss, dehydration or malnutrition	Inadequate oral caloric or fluid intake; tube feeding, TPN, or hospitalization indicated	-

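### The solicited systemic holding rule in Section 6.5 conflicts with itself and with the fever grades in Appendix 14.5, and non-serious solicited systemic reactions starting after its 3-day window trigger no automatic hold

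*Supplement*

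**What the plan says.** All references are to protocol V1.4 of 08.03.2021. Section 6.5 lists four holding rules.

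| Rule | Threshold | Entry grade | Persistence (> 48 h) | Onset |
|---|---|---|---|---|
| Solicited local | > 30% of injections | ≥ 3 (swelling, pain); 4 (redness) | 3 (swelling, pain); 4 (redness) | any time |
| Solicited systemic | > 25% of injections | 3 | ≥ 3 | injection day and next 2 days |
| Unsolicited | > 25% of volunteers | ≥ 3, probably or definitely related | 3 | none stated |
| SUSAR | one event | life-threatening or fatal | not applicable | none stated |

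The systemic rule counts an injection that is "followed by Grade 3 solicited systemic AE beginning within 3 days after study injection (day of injection and 2 subsequent days"). The local rule carries a different onset clause: "Grade 4 redness (first occurrence at any time after vaccination"). The section begins by limiting all four: "Safety holding rules for each subject will apply throughout the study period until interim safety analysis (V4"). V4 is day 28 ± 2.

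Appendix 14.5 defines Grade 3 fever as "≥ 40.0°C for ≤ 24 hours" and Grade 4 fever as the same temperature for at least 24 h.

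Section 2.1.1 sets the collection periods. For solicited events it reads "Solicited: ADRs/AEs occurring from the time of each injection throughout 28 days following the procedure". Unsolicited AEs run to day 56 and SAEs to the final visit.

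Under Section 6.5 an active hold blocks vaccination in the next study phase until the DSMB approves, yet the same section describes how injections are resumed. Section 3 divides the trial into two parts and says that Part II volunteers are treated simultaneously.

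**The concern.** These percentage rules are the only preset, mandatory brake for reactions that are severe but not serious. The stopping rule and the SUSAR rule both require seriousness.

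A site or an eCRF programmer who applied the systemic rule would have to decide several things that the text leaves open or answers in two ways:

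- whether a long fever counts;
- whether Grade 4 at onset counts;
- which rule covers a solicited term that starts on day 4 or later;
- which injections form the denominator;
- what a hold would pause once Part II has begun.

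At stake is whether a cluster of non-serious severe systemic reactions in adults aged 56-80 leads to a pause by rule or only by someone's judgement.

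**Working it through.** **1. The plan's own figure.** The protocol gives no operating characteristics for the holding rules. Its one safety calculation is the one-SAE rule (Section 8.1.1), and it reproduces. Power is 1 − (1 − 0.05)^33 = 0.816. Actual alpha is 1 − (1 − 0.0001)^33 = 0.0033, stated as 0.003. Allowing for dropout, 33 / 0.925 = 35.7, so 36.

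**2. Fever.** Let d be the time at or above 40.0 °C.

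- Grade 3 needs d ≤ 24 h and persistence needs d > 48 h. No value of d meets both.
- For d > 48 h the final grade is 4. If grading follows the event as it evolves (Grade 3 first, then Grade 4), the entry clause is met and the persistence clause admits the rest. If the event is graded once by total duration, it is Grade 4 and the literal entry clause leaves it out. Footnote 11 of Table 1 requires changes of grade to be reported, but Section 6.5 does not say which grade counts.
- Grade 4 fever in Appendix 14.5 is defined by duration. It is therefore not automatically an SAE under Section 9.1.5.

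**3. Onset.** The systemic window covers 3 of the 28 solicited days. An event from the solicited list (Section 9.1.2) that starts after the window but by day 28 fails the systemic rule on timing and the unsolicited rule on type.

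**4. Effect of the window in Part II.** Assumptions: n = 24, counted by part, independent volunteers, and p the rate of qualifying non-serious events. More than 25% of 24 means floor(0.25 × 24) + 1 = 7. Without the window, P(X ≥ 7) uses Binomial(24, p). With half the onsets late, the rule as written uses Binomial(24, p/2).

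| p (assumed) | As written, all late | As written, half late | No window |
|---|---|---|---|
| 20% | 0 | 0.01 | 0.19 |
| 30% | 0 | 0.06 | 0.61 |
| 40% | 0 | 0.19 | 0.90 |

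**5. Serious events.** The one-SAE rule has no onset window and no V4 limit. P(at least 1 associated SAE in 24) = 1 − (1 − q)^24 = 0.38, 0.71 and 0.92 for q = 2%, 5% and 10%.

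**6. Denominator.** Counted by part, more than 25% is 7 of 24. Pooled over the trial it is floor(0.25 × 36) + 1 = 10 of 36. The text does not choose.

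**7. End of cover.** The rules stop for each subject at V4, while unsolicited AEs are collected to day 56. Unsolicited AEs on days 29-56 are therefore under no holding rule.

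**8. What is held.** The blocked object is a following study phase. After Part II there is none.

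**The case against.** A reader might infer that nothing would pause Part II. The documents do not support that.

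- One associated SAE meets the stopping rule (Sections 8.2 and 8.6).
- The unsolicited and SUSAR holding rules remain.
- Section 8.6 allows termination for an unacceptable AE profile.
- Section 1.4 allows an emergency DSMB meeting at any time.

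The last two are discretionary, so they do not replace an automatic hold.

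A reader might also infer that no Grade 4 reaction can count. That is too broad. An event that enters at Grade 3 and worsens still qualifies. Among systemic terms Appendix 14.5 gives a Grade 4 only for fever, vomiting and diarrhea; for the latter two it means life-threatening consequences, which is an SAE. Section 9.1.2 offers the appendix as guidance. A fever too brief to meet the 48 h condition is excluded by design. The problem is the longer fever, whose grade then no longer matches the entry clause.

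The V4 limit does not contradict the local rule's open onset clause. It bounds that clause, runs per subject and matches the 28-day solicited period.

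The depot might seem to predict late toxicity. Section 1.1.3.2 does say "This granuloma further increases up to 8ml on day 17 after vaccination" and that "a gradual release of these peptides or XS15 into the blood can be expected", but it uses these points to argue for dilution and low blood levels and concludes that systemic toxicity is not expected. Part I to day 28 showed no relevant systemic effects. The gap therefore rests on the wording of the rules, not on a forecast of late toxicity.

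Two larger figures should not be used. That 25 of 28 days (89%) lie outside the window is not a share of risk, because it weights all days equally. A requirement of 10 of 24 (42%) in Part II presumes pooling with an event-free Part I, which the text does not state.

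The strongest remaining objection is practical. If all 24 volunteers are dosed at nearly the same time, a hold has little left to pause. Section 3 refers to Figure 3 for the sequence, and the figure was not available in the copy examined. Section 6.5 itself presumes that further injections may follow.

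**Conclusion.** The concern holds in a limited form. Two points follow directly from the text. The systemic rule uses two different grade conditions in one sentence and conflicts with the fever grades in Appendix 14.5. Non-serious Grade 3 solicited systemic events that start after the 3-day window, but within the solicited period, trigger no automatic hold. Three lesser points are also open: the denominator (7 of 24 or 10 of 36), unsolicited AEs on days 29-56, and what a hold pauses in Part II.

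The probabilities (0 against 0.61 or 0.90 if all onsets are late) depend on assumed rates of 30-40%, a by-part count and independence. They show how the rule behaves; they do not predict events. The benefit of any hold also depends on how Part II dosing is staggered. With the one-SAE stop and DSMB oversight in place, this is a correction worth making, but not a flaw that undermines the trial.

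**What to change.** Reconcile Section 6.5 with Sections 2.1.1 and 3 and with Appendix 14.5 on six items:

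1. the entry grade against the persistence grade, and against the entry wording of the other rules;
2. the persistence condition against the fever grades, including which grade counts when it changes;
3. the systemic onset window against the 28-day solicited period, stating which rule, if any, covers later solicited events;
4. the end of applicability against the 56-day unsolicited period;
5. the denominator;
6. what a hold pauses once Part II is under way.

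The sponsor and DSMB set the values; none is proposed here. The DSMB charter and the eCRF alert should then match the text.

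The cost is protocol wording, charter alignment and a revised alert, with no extra visits or data. The downside is a possible pause that would not otherwise occur.
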